## 2.5 Study Population

Any individual who meets the inclusion and exclusion criteria will be eligible for enrollment, regardless of gender, race, ethnicity, or national origin.

#### 2.5.1 Inclusion Criteria

- 1) Patients with end stage renal disease requiring chronic renal replacement therapy
- 2) Age  $\geq$  13 years
- 3) Achieved mean eKt/V of  $\geq$  1.0 on at least two baseline sessions
- 4) Weight  $\geq$  30 kg

## 2.5.2 Exclusion Criteria

- 1) Residual renal urea clearance > 3 mL/min per 35 L
- 2) Expectation that native kidneys will recover
- 3) Vascular access being used for HD is a non-tunneled catheter
- 4) Inability to come for in-center 6 days a week, including inability to arrange adequate transportation
- 5) History of poor adherence to thrice weekly HD
- 6) Medical conditions that would prevent the subject from performing the cardiac MRI procedure (e.g., inability to remain still for the procedure, a metallic object in the body, including cardiac pacemaker, inner ear (cochlear) implant, brain aneurysm clips, mechanical heart valves, recently placed artificial joints, and older vascular stents)
- 7) Unable to verbally communicate in English or Spanish
- Requires HD > 3 times per week due to medical co-morbidity (such as, but not limited to: systemic oxalosis or requiring total parenteral nutrition). Occasional ultrafiltration on a fourth day per week is not an exclusion criterion.
- 9) Currently on daily or nocturnal HD, or less than 3 months since the subject discontinued daily or nocturnal HD
- 10) Scheduled for living donor kidney transplant, change to peritoneal dialysis, home HD, or plans to relocate to another center within the next 14 months
- 11) Expected geographic unavailability at a participating HD unit for > 2 consecutive weeks or > 4 weeks total during the next 14 months (excluding unavailability due to hospitalizations) (frequent HD subjects who leave for vacation may resort back to conventional HD during these time periods)
- 12) Less than 3 months since the patient returned to HD after acute rejection resulting in allograft failure
- 13) Currently in acute or chronic care hospital
- 14) Life expectancy < 6 months

- 15) A medical history that might limit the subject's ability to take trial treatments for the 12 month duration of the study, including: currently receiving chemo or radiotherapy for a malignant neoplastic disease other than localized non-melanoma skin cancer, active systemic infection (including tuberculosis, disseminated fungal infection, active AIDS but not HIV, and cirrhosis with encephalopathy)
- 16) Current pregnancy, or actively planning to become pregnant in the next 12 months
- 17) Contraindication to heparin, including allergy or heparin induced thrombocytopenia
- 18) Current use of investigational drugs or participation in another clinical trial that contradicts or interferes with the therapies or measured outcomes in this trial
- 19) Unable or unwilling to follow the study protocol for any reason (including mental incompetence)
- 20) Unable or unwilling to provide informed consent or sign IRB-approved consent form

#### 2.6 Screening Evaluation

The purposes of the screening evaluation are to identify potential study subjects for trial enrollment, to provide potential study subjects with information regarding the study, to obtain written informed consent for participation and randomization. The length of the screening evaluation will generally be 2-12weeks.

A trained study coordinator for each study site will consult with physician investigators and collaborators to determine whether patients who have recently developed ESRD, or who are scheduled to begin HD within the next several weeks, will be appropriate candidate subjects for the study. For existing patients at study facilities, the physician investigators, collaborators and study coordinators may review on-site medical records to determine potential trial eligibility. The physician investigator, collaborator or study coordinator will approach patients deemed eligible and will provide patients with verbal and written information regarding the study. Other resource materials, including study brochures will be provided to potential candidates. If the patient is agreeable, written informed consent to conduct a detailed baseline assessment and undergo randomization will be obtained and the patient will be asked to sign an Institutional Review Board - approved consent form, along with a form allowing for the use of personal health information. A written informed consent will be obtained for the storage of blood for future biochemical testing.

#### 2.7 Baseline Evaluation

The purposes of the baseline evaluation are to provide subjects with further information regarding the study, collect detailed data on eligibility and exclusion criteria (including practical issues such as transportation), and document baseline characteristics and clinical information to allow stratification and assessment of important baseline prognostic variables, as well as enable pre- and post-study comparisons of specific outcomes between treatment groups. *[2014 FHN Archive Note: FHN Executive Committee dropped prognostic covariates from the analyses.]* In addition, some of the characteristics assessed will enable observational comparisons with the Nocturnal Study being conducted in parallel with this trial. The length of the baseline evaluation period will be three to fifteen weeks.

Baseline Visits will be labeled as B1 visits. The baseline assessment will include two kinetic modeling sessions, separated by at least one week (see Section 3) and labeled as the B1 and B2 visits. Key biochemical tests, including predialysis serum albumin and pre- and post-dialysis serum urea nitrogen, creatinine, and phosphorus will be obtained from local laboratories for both baseline kinetic

modeling sessions. Derived kinetic modeling parameters and the pre-dialysis albumin and phosphorus concentrations will be averaged to determine the actual assigned baseline value. A timed urine collection (minimum 18 hours) will be obtained during the interdialytic interval preceding a dialysis session, preferably midweek for subjects producing urine prior to a baseline kinetic modeling session for evaluation of the residual renal function exclusion criterion. During the baseline period, participants will also be asked to travel to and from the HD unit for 6 consecutive days (i.e., on 3 HD days and on 3 intervening non-HD days), to determine if they are able to arrange and tolerate daily travel should they be randomized to the frequent arm of the trial. On the days subjects travel to and from the dialysis unit but do not receive dialysis (before randomization), they will not be required to stay at the dialysis unit for an extended period.

Comorbidities will be assessed at baseline using the modified Charlson comorbidity index [Hemmelgarn, 2003], supplemented by additional questions from the Index of Co-existing Disease Score [Miskulin, 2001]. The majority of baseline HRQL surveys will be administered by telephone through the Central HRQL Survey Center. Measures requiring visual and motor assessment will be administered by the Clinical Center's study coordinator. A baseline measurement of left ventricular mass index by MRI will be obtained at designated MRI facilities for the study and read by a Central reading center. Additional baseline measurements are described in Section 6.

Once the baseline evaluation is completed, subjects will be re-evaluated by the study coordinator for eligibility to undergo randomization. If the patient is deemed eligible, the study coordinator will review the implications of randomization with the patient, and confirm the subject's desire to undergo randomization. For subjects choosing not to be randomized, or deemed ineligible for randomization at any time during the baseline period, a baseline dropout form will record the reason for dropout.

All baseline case report forms, including valid results for each of the primary and main secondary endpoints must be entered into the database in order for a subject to be randomized.

# 2.8 Randomization of Trial Participants

Once the baseline evaluation is completed and eligibility is verified, consenting subjects will be randomly allocated in a 1:1 allocation to conventional or daily HD. The randomization schedules will be prepared by the Data Coordinating Center (DCC) prior to the start of recruitment.

Randomization will be stratified by Clinical Center and by diabetes status. Randomly permuted blocks of random sizes will be used to help balance numbers of participants assigned to both treatment regimens. This method guarantees that at no time during randomization will the participants in the individual groups be grossly unequal.

The randomization process will be centrally administered. All randomization schedules will remain confidential and known only by members of the Data Coordinating Center staff.

Once all baseline period studies have been completed, the forms corresponding to these studies have been received by the Data Coordinating Center, and the forms have been checked to be sure the patient meets eligibility requirements, the Principal Investigator or the study coordinator shall access the interactive randomization program. The program will verify through a defined set of questions that the participant is eligible and ready to be randomized and provide a randomized treatment assignment for that participant based upon his or her stratum. The randomization assignment will be displayed on the screen and emailed to the Clinical Center.

Randomization marks the participant's official and irrevocable entry into the Follow-up Period. Once a participant has been randomized, efforts will be made to conduct all evaluations irrespective of whether the subject starts the study treatment regimen or not, how long the patient continues on the

study treatment regimen, and how well the patient adheres to the study treatment regimen (see Section 7). These efforts should continue until termination of the Follow-up Period.

# 3. Intervention Plan

# 3.1 Description of the Intervention: Dialysis Frequency and Dose

## 3.1.1 Summary of the Dose Intervention

Consenting patients meeting eligibility criteria will be randomized to one of two HD regimens:

- i) Conventional hemodialysis of 3 sessions per week. Subjects may remain on their usual dialysis prescription subject to a minimum eKt/V of 1.1 per session and a minimum treatment time of  $\geq$ 2.5 hours per session;
- ii) *Daily hemodialysis* of 6 sessions per week, to maintain a target  $eKt/(V_n)^*$  of 0.90 per session, and a treatment time of 1.5 hours to 2.75 hours.\*\*

# $*V_n =$ "normalized V" = 3.271 × V(2/3)

\*\*If a patient is unable to achieve the target  $eKt/(V_n)$  of 0.90 within 2.75 hours, the patient's target  $eKt/(V_n)$  will be reduced to that which can be achieved within a treatment time of 2.75 hours. If necessary, the maximum treatment time may be exceeded in order to maintain an ultrafiltration rate of <1.0 L per hour, or upon the discretion of the treating nephrologist for clinical reasons.

Although the dose target for the daily HD arm is expressed in terms of urea clearance, by varying both treatment frequency and total weekly treatment time the design is intended to achieve a large separation in the clearance of a wide range of solutes and in volume stability (see Table 3 below). In particular, the projected separation in total weekly treatment time (median 14.2 hours for the daily HD group vs. 10.5 hours for the conventional HD group) will result in a separation between dose groups in clearance of middle-molecular weight solutes in addition of small molecular weight solutes such as urea. The study design is not intended to determine the effects of each specific component of the daily HD treatment regimen, but rather is based on the pragmatic objective of determining whether the combination of factors associated with the daily HD regimen can improve outcomes. If subjects in the daily HD arm develop an unwillingness or inability to follow the 6x/week treatment regimen specified by the protocol, efforts will be made to adopt a reduced treatment regimen which approximates the intended 6x/week regimen as closely as possible (see Table 7 of Section 3.1.6).

# 3.1.2 Rationale for Choosing Target Doses

# a) Conventional HD Group

HD dosing is traditionally based on clearance of urea, quantified as the Kt/V (K is the clearance of urea, t is time of dialysis session, and V is the volume of distribution of urea in the patient). Traditionally the single-pool Kt/V (spKt/V) has been used to define and measure dose in conventional HD [Gotch, 1985]. However, because the spKt/V overestimates true clearance due to the phenomenon of urea rebound, this trial will use equilibrated Kt/V (eKt/V) [Daugirdas, 1995;Pedrini, 1988]. In order to assure adherence to current national standards, a minimum eKt/V of 1.10 will be required in the conventional HD group. However, consistent with its designation as a conventional therapy arm, the dialysis prescriptions in the conventional HD group will be otherwise unspecified (subject to a minimum treatment time of 2.5 hrs).

Parameter	Conventional HD (CHD)	Daily HD (DHD)	% Difference in Medians (DHD vs. CHD)
Sessions per week	3	6	100%
Target prescription	Unspecified: $eKt/V \ge 1.10$	$eKt/(V_n) = 0.90$	-
Hours per session	$\geq 2.5$ (median = 3.50)	1.50 to 2.75 (median = 2.36)	-33%
Maximum interdialysis interval (median, hours)	68.5	45.6	-33%
Average interdialysis interval (median, hours)	52.5	25.6	-51%
Hours per week	10.5	14.2	2514
(median, $5^{th} - 95^{th}$ percentile)	(9.0-13.1)	(11.5 – 16.5)	+35%
eKt/V urea per treatment	1.39	0.92	2.40/
(median, $5^{th} - 95^{th}$ percentile)	(1.12 – 1.75)	(0.74 – 1.05)	-34%
Weekly stdKt/V urea	2.46	3.82	. 550/
(median, $5^{th} - 95^{th}$ percentile)	(2.16 – 2.80)	(3.32 – 4.17)	+55%
Weekly eKR $\beta_2$ -microglobulin (ml/min per 35 L total urea volume) (median, 5 th – 95 th percentile)	4.80 (3.77 – 6.21)	5.43 (4.26 – 6.85)	+13%
Standardized phosphorus removal (mg/day) (median, 5 th – 95 th percentile)	299 (254 - 374)	415 (338 – 497)	+39%

#### Table 3: Summary of the Dose Treatment Regimens

eKt/V = equilibrated Kt/V, stdKt/V = standard weekly Kt/V, eKR = continuous equivalent renal clearance Medians, 5th, and 95th percentiles based on simulations assuming distributions of patient characteristics and baseline dialysis prescriptions from the Renal Research Institute Database, n=3285.

#### b) Daily HD Group

#### *i*) Rationale for Factoring Kt by Vn

The rationale for factoring Kt by  $V_n$  rather than V involves pragmatic and physiological considerations. From a pragmatic perspective, factoring Kt by  $3.271V^{(2/3)}$  rather than V reduces the effect of large V's on calculation of Kt/V, resulting in moderately higher eKt/V's for smaller patients

and moderately lower eKt/V's for larger patients (Table 4). In addition, empiric data from 3285 patients associated with the Renal Research Institute (RRI) suggests that this adjustment corresponds to current practice patterns at these dialysis units (Table 5). The final row of Table 5 indicates that mean eKt/( $V_n$ ) is approximately constant for different values of V, whereas mean eKt/V declines as V increases.

Patient Weight (kg) (assuming weight = V/0.6)	Patient V (L)	eKt /(V n )	eKt/V
42	25	0.90	1.01
50	30	0.90	0.95
58	35	0.90	0.90
67	40	0.90	0.86
75	45	0.90	0.83
83	50	0.90	0.80

Table 4:	Achieved	eKt/V f	or Different	V's when	$eKt/(V_n) = 0.90$
----------	----------	---------	--------------	----------	--------------------

Table 5: Relationship of Treatment Time, eKt/V, and eKt/(Vn) to Patient Volume (V)\*

Patient V (L)	Treatment Time (min)	eKt/V	eKt/(V n )
< 27.5	189	1.51	1.35
27.5 - 32.5	202	1.43	1.36
32.5 - 37.5	212	1.35	1.34
37.5 - 42.5	224	1.29	1.35
> 42.5	240	1.21	1.34

\*N=3285 from RRI database

From a physiologic perspective, factoring Kt by V raised to a power less than 1 is justified by the argument that toxin generation may be more directly related to body surface area rather than to volume. Native renal clearance is traditionally standardized to body surface area rather than volume of body water. The exponent of 2/3 is suggested by the physical relationship that the surface area of a 3-dimensional body is approximately proportional to volume raised to the 2/3 power.

ii) Rationale for Choosing Target  $eKt/(V_n) = 0.90$ 

The target  $eKt/(V_n)$  of 0.90 was determined as providing the maximum separation that could be achieved between the daily HD and the conventional HD treatment groups for a wide range of parameters related to solute clearance, treatment time, and volume while only modestly increasing total weekly treatment time in the daily arm.

## 3.1.3 Calculation of eKt/V and eKt/(Vn)

Single pool Kt/V will be calculated by applying the 2-BUN algorithm [Depner, 1989] to the predialysis and post-dialysis ureas collected according to current K/DOQI standards. For the Conventional HD group, the modification of the method of the Tattersall rate equation developed in the HEMO Study [Daugirdas, 2004] will be used to estimate eKt/V from spKt/V according to the formula:

$$eKt/V = spKt/V \times (T/(T+30.7))$$
 (EQ 1)

where T denotes treatment time in minutes. Additional calculations based on equation 1 will be used to obtain an estimate of the actual (2-pool) V from the single pool V derived from the 2-BUN method. To minimize the risk that errors in modelled V would affect the dialysis dose, when determining dialysis prescriptions in the daily HD group eKt/(Vn) will be computed as [eKt/V] ×  $3.271^{-1} \times [Vant]^{(1/3)}$ , where Vant is the anthropometric volume estimated using the Watson formula. Details are provided in the Manual of Operations.

#### 3.1.4 Data Collection, Determining the Initial Prescription, and Monitoring of Dose

Data to be obtained at kinetic modeling sessions are summarized in Table 6. Although kinetic modeling data will be obtained monthly in order to characterize the interventions, the protocol for establishing and updating dialysis prescriptions is designed to minimize the number of prescription modifications. The protocol for measurement of residual renal function is described in Section 3.1.5.

Treatment date
Start and end times (recorded)
Actual treatment time recorded on the dialysis machine, if available
Dialysate flow
Blood flow
Dialyzer membrane type
Reuse number
Interruption status (was total interruption time >15 min?)
Intradialysis hypotensive episodes and other symptoms requiring saline or reduced UF
Pre and Post HD systolic and diastolic blood pressure
Pre and Post HD weight
Pre and Post HD urea (local laboratory measurement)
Pre and post HD creatinine (local laboratory measurement)
Pre and post HD phosphate (local laboratory measurement)
Predialysis serum $\beta_2$ -microglobulin (to be measured in reposited serum specimens)
Predialysis serum albumin (local laboratory measurement)

\* In addition to data collection from the kinetic modeling session itself, start and end times, pre and post HD weights, predialysis blood pressures, and intradialytic hypotensive episodes leading to treatment interruptions will also be obtained from the dialysis run sheet for all HD sessions during the week preceding the kinetic modeling session once during baseline and monthly during follow-up.

a) Baseline Kinetic Modelling Sessions

Two kinetic modelling sessions, designated B1 and B2, will be conducted during the baseline evaluation phase of the trial. The two sessions will be spaced at least one week but no more than six weeks apart.

If the coefficient of variation of the estimates of urea distribution volume (V) from the two baseline kinetic modeling sessions (B1 and B2) differs by 20% or more, a third baseline kinetic modeling session (labeled B3) will be required. The median of all baseline urea volume estimates will be used to determine the initial post-randomization dialysis prescription.

In order to prevent randomization of patients who are unable to achieve an eKt/V close to the minimum level of 1.10 in the conventional HD arm, subjects must achieve a mean eKt/V of at least 1.00 on the final two baseline kinetic modeling sessions in order to be randomized. If the mean eKt/V for the final two of the baseline kinetic modeling indicated above is less than 1.00, then an additional kinetic modeling session may be scheduled, and the mean eKt/V recomputed from the last two baseline sessions. This process may be repeated up to 4 times, and the minimum eKt/V requirement will be met if at any of these tries the average eKt/V for the final two assessments exceeds 1.00. The baseline minimum threshold of 1.00 is set 0.10 eKt/V units below the minimum eKt/V of 1.10 in the conventional HD arm, to take into account the random variation that can be expected from the average eKt/V over two modeling sessions.

## b) Determining and Monitoring the Trial Prescription during Follow-up

## *i)* Conventional HD Group

Subjects randomized to the Conventional HD group may follow any dialysis prescription provided their prescribed eKt/V is at least 1.10 and treatment time is at least 2.5 hours. Modeling data will be obtained monthly. The prescribed eKt/V will be computed centrally based on the subject's current running median V over the preceding 4 months, and the subject's current blood flow, dialysate flow, dialyzer type and ultrafiltration rate. If the prescribed eKt/V falls below 1.10, the Data Coordinating Center will e-mail a warning to the study coordinator at the patient's Clinical Center that includes the patient's study ID number and the patient's prescribed eKt/V, and provide alternative prescription options for a prescribed eKt/V of at least 1.10.

# ii) Daily HD Group

At randomization, the Data Coordinating Center will send an array of dialysis prescription options for a target  $eKt/(V_n)$  of 0.90 in which the treatment times are between 1.5 and 2.75 hours. Subsequently, modeling data will be obtained monthly, and revised dialysis prescriptions will be provided if the running median V (over 4 months) increases by an amount that leads to a decrease in the updated prescribed  $eKt/(V_n)$  to a value less than 0.75. Failure to implement the revised prescriptions will be regarded as non-adherence to the protocol. This procedure is designed to assure that the running median achieved  $eKt/(V_n)$  does not fall more than 0.15  $eKt/(V_n)$  units below that 0.90 target throughout follow-up.

The Data Coordinating Center will also send a revised prescription if the running median V changes by an amount that leads to an increase in the prescribed  $eKt/(V_n)$  to a value greater than 1.05. In this case, reductions in dialysis dose in accordance with the revised prescription will be at the discretion of the treating nephrologist.

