## 3.1.6 Non-adherence and Deviations from the Protocol

If during follow-up subjects randomized to 6x/week therapy are unwilling or unable to continue to follow their 6x/week dialysis prescriptions stipulated by the protocol, efforts will be made to approximate the target 6x/week prescription as closely as possible with a revised prescription with either reduced total weekly treatment time or with a reduced frequency of dialysis sessions. The hierarchy of alternative options outlined in Table 7 below will be followed for patients unwilling or unable to adhere to the protocol 6x/week regimen.

In the event of a deviation from the 6x/week schedule specified by the protocol, the Clinical Center's personnel will consult with the study subject in an effort to adopt the highest option in the above table. If one of Options 1-4 is adopted, the Clinical Center's staff will periodically discuss the treatment options with the patient to determine if the patient is willing or able to return to a higher Option number, or ideally to return to the full 6x/week regimen specified by the protocol. Missed treatments will be monitored closely to ensure the safety of trial participants (Section 3.2).

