#### 3.3 Methods to Protect Against Bias

Guidelines for dialytic and non-dialytic co-interventions have been stipulated (see Section 3.4) to reduce the risk that health care team enthusiasm for the novel therapy of daily HD may lead to differences in care between the treatment groups. To reduce the risk that study personnel may influence patient responses to questionnaires, the HRQL, depression, and utility questionnaires will be administered centrally over the telephone by trained interviewers who are blinded to the patient's treatment assignment. Secondary outcomes that require in-person interviewer survey assessment will be administered by a study coordinator using standard scripts.

Option Number	Description of Option
1	Maintain 6x/week treatment schedule, but reduce treatment time to the projected total weekly treatment time or an amount acceptable to the patient, subject to: a) minimum session length $\geq$ 1.5 hours, b) total weekly treatment time $\geq$ total weekly treatment time the patient would have had if assigned to the conventional HD group.
2	Adopt a $5x$ /week treatment schedule, but increase treatment time to the maximum amount acceptable to the patient such that the projected weekly stdKt/Vurea approximates the patient's target stdKt/V urea as closely as possible.
3	Adopt a 5x/week treatment schedule, without increasing the time per treatment, so long as a) minimum session length $\geq$ 1.5 hours, and b) total weekly treatment time $\geq$ total weekly treatment time the patient would have had if assigned to the conventional HD group.
4	Adopt a 4x/week treatment schedule, but increase treatment time to the maximum amount acceptable to the patient such that the projected weekly stdKt/Vurea approximates the patient's target stdKt/Vurea as closely as possible.

Table 7:	Stepped	Options for	Modifying	6x/Week	Daily HD	Regimen
----------	---------	--------------------	-----------	---------	----------	---------

Patients on daily HD may perceive improvements in their HRQL which have more to do with the novelty of the therapy than to its true benefits ('honeymoon effects'). However, HRQL benefits due solely to the novelty of daily HD would not be expected to persist over 1 year. For this reason, the HRQL outcomes will be assessed at months 4 and 12. In addition, at month 12, an assessment of health expectations will be made.

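### The daily-arm dose rule in Section 3.1.4 is meant to hold the achieved eKt/(Vn) within 0.15 of 0.90, but its lower trigger acts only on the prescribed value, through a rise in V

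*Protocol*

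**What the plan says.** Section 3.1.4 b) ii) of the protocol sets the daily-arm target eKt/(Vn) at 0.90. A revised prescription follows "if the running median V (over 4 months) increases by an amount that leads to a decrease in the updated prescribed" eKt/(Vn) to below 0.75, and failing to implement it counts as non-adherence. The section then gives the purpose: "This procedure is designed to assure that the running median achieved" eKt/(Vn) does not fall more than 0.15 below 0.90 at any time in follow-up. A second trigger, at a prescribed value above 1.05, concerns overdosing and does not bear on the floor.

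Related text:

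- Section 3.1.4 (opening): modeling is monthly, but the prescription protocol "is designed to minimize the number of prescription modifications".
- Section 3.1.3: "when determining dialysis prescriptions in the daily HD group", eKt/(Vn) is computed from eKt/V and the anthropometric (Watson) volume.
- Section 3.1.1, second footnote: for a patient who cannot reach 0.90 in the permitted time, the target "will be reduced to that which can be achieved within a treatment time of 2.75 hours". No lower bound is given. Section 3.1.4 b) ii) does not mention such targets.
- Section 3.1.6 and Table 7: stepped alternatives for daily patients who "are unwilling or unable to continue to follow their 6x/week dialysis prescriptions stipulated by the protocol".
- Section 7.2: the conventional arm is reviewed when eKt/V of 1.10 is not met on 2 or 3 consecutive measurements. The daily arm is reviewed when stdKt/V of 2.0 is not met on 3 consecutive measurements. Persistent nonadherence is also reviewed, but its definition is left open.

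**The concern.** The stated purpose concerns achieved dose and the trigger concerns prescribed dose. They differ whenever a patient does not receive what was prescribed. The rule compensates for one cause of underdosing, growth in V. It does not respond to another that the protocol itself foresees in Section 5.2.4: patients who tire of the schedule and shorten their sessions.

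Section 3.1.1 makes a large separation in solute clearance an aim of the design. A daily patient whose achieved value stays below 0.75 remains in the intention-to-treat comparison, as is right. If no dose alert is raised, a shortfall that might have been corrected is not, and the contrast between the arms is somewhat smaller than the text suggests.

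A second, smaller defect lies in the same paragraph. The 0.90 and 0.75 figures apply to everyone, including patients whose target was lowered under Section 3.1.1.

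**Working it through.** **Inputs.** Target 0.90, lower trigger 0.75 and margin 0.15 (Section 3.1.4 b) ii)). Daily session length "1.50 to 2.75 (median = 2.36" h) from Table 3, so the median is 2.36 × 60 = 141.6 min. EQ 1 (Section 3.1.3): eKt/V = spKt/V × T/(T + 30.7), with T in minutes.

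**The plan's own figures.** 0.90 − 0.15 = 0.75 and 0.90 + 0.15 = 1.05. Both triggers reproduce.

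**What fires the rule.** By Section 3.1.3, eKt/(Vn) = eKt/V × Vant^(1/3) / 3.271. With Vant fixed, it varies inversely with modeled V. Going from 0.90 to 0.75 therefore needs V to rise by a factor of 0.90/0.75 = 1.20, a 20% rise.

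**What recorded shortening does.** A session known to be short enters the model with its true time, so modeled V is not inflated and the prescribed value does not move. The achieved value falls as follows.

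- *EQ 1, constant clearance.* EQ 1 is given for the conventional group, so using it here is an assumption. Then eKt/(Vn) = c × T²/(T + 30.7). At T = 141.6, T²/(T + 30.7) = 20,050.6/172.3 = 116.4, so c = 0.90/116.4 = 0.00773. At T = 121.5, 14,762/152.2 = 97.0, and 97.0 × 0.00773 = 0.75. The cut is 141.6 − 121.5 = 20.1 min (14%).
- *Simple proportion.* 141.6 × 0.75/0.90 = 118.0 min, a cut of 23.6 min (17%).
- *Other session lengths, EQ 1.* From 90 min the cut is 12.1 min; from 165 min it is 23.9 min.

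Shortened sessions of 118 to 121.5 min still lie inside the permitted 90 to 165 min.

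Smaller shortfalls suffice once V has drifted part of the way. Prescribed 0.80 with 10% under-delivery gives 0.80 × 0.90 = 0.72. Prescribed 0.76 with 5% under-delivery gives 0.76 × 0.95 = 0.72. Neither fires the rule.

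Because the stated bound is on a running median, occasional short sessions do not breach it. The shortening has to be sustained across the modeling sessions in the window.

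**The other dose check.** The daily-arm limit in Section 7.2 is stdKt/V 2.0. Table 3 projects medians of 3.82 (daily) and 2.46 (conventional), with a conventional 5th percentile of 2.16. The limit thus lies below nearly the whole projected conventional range. It guards against underdialysis and cannot indicate loss of separation.

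**Reduced targets.** The protocol gives no values, so take 0.80 as an illustration. The fixed trigger fires after a V rise of 0.80/0.75 − 1 = 6.7%. A target below 0.75 would be under the trigger from the start. A patient already at 2.75 h may be unable to follow the revised prescription, yet not implementing it counts as non-adherence. With the trigger at target minus 0.15, the level for this patient is 0.65 and the V rise needed is 0.80/0.65 − 1 = 23%, close to the 20% for a patient at 0.90.

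**The case against.** The best defense is that the paragraph is about setting prescriptions, and that patients who cut sessions short are dealt with elsewhere. Shortened and missed sessions are counted monthly (Section 5.2.4, Table 11F), run-sheet start and end times are collected for a week each month, the Recruitment and Adherence Committee reviews persistent nonadherence (Section 7.2), and Table 7 offers alternatives. A new prescription does not cure a refusal to complete the present one. The wording states a design intent, and replacing achieved with prescribed would remove the contradiction.

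Much of this stands. A reader might infer that nothing in the protocol would notice a daily patient's low achieved dose. That is not so: stdKt/V is checked on measured values, and shortening is recorded and can be reviewed. What remains is narrower. None of these checks uses 0.75, and the definition of persistent nonadherence is open.

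Three other inferences are not supported:

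- *That a recorded fall in blood flow escapes the rule.* For the conventional arm, Section 3.1.4 b) i) computes the prescribed value from current flows as well as V. The daily paragraph does not say how its updated value is computed; if it is done the same way, lower recorded flow would reduce it. Clearance losses not visible in recorded time or flow inflate modeled V and may also fire the rule.
- *That low doses under Table 7 are an undetected gap.* They are agreed compromises with known patients. The floors in Options 1 and 3 are deliberately on time, including the "total weekly treatment time the patient would have had if assigned to the conventional HD group".
- *That reduced targets cost separation, or affect a share of patients that Table 3 reveals.* The fixed 0.75 makes the rule fire sooner for them. Table 3 does not show who has a reduced target, and being at the time cap is not the same thing.

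**Conclusion.** The point holds in a limited form. The daily-arm rule does not deliver the property stated for it: recorded shortening with stable V can hold the achieved running median below 0.75 without a dose alert. At the median session this takes a sustained loss of about 20 to 24 min, the lower figure resting on EQ 1 carrying over to the daily arm. The conventional arm, by contrast, is reviewed against its own floor.

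The documents do not allow an estimate of how many patients would be affected. A reader might infer that the trial's error rate or primary analysis is compromised; neither is touched. The consequence is confined to dose monitoring, to the chance of correcting lost separation during the trial, and to which patients are labeled non-adherent. The weight is low to moderate: worth correcting because the correction is cheap.

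**What to change.** 1. In Sections 3.1.4 and 7.2, add a Data Coordinating Center action item for when the 4-month running median achieved eKt/(Vn) is more than 0.15 below the patient's current target (0.90, or the target reduced under Section 3.1.1).
2. Route it by cause: to a revised prescription if the prescription is the cause, or to adherence review and Table 7 if shortened sessions are. Flag a patient on an agreed Table 7 option once only.
3. Restate the V trigger as the patient's current target minus 0.15, so that a patient at the 2.75 h cap is not sent a prescription that cannot be met and then counted as non-adherent.
4. Word the stated purpose to match, relative to the current target. For a reduced target the level will lie below 0.75 (0.65 for a target of 0.80), and the text should say so.
5. Keep the stdKt/V 2.0 review as a separate safety limit.

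The cost is a few sentences, some programming and a few more alerts. The modeling data are already collected monthly, and the 4-month median respects the aim of few prescription changes. One limit remains: modeling sessions will not show shortening confined to other sessions, for which the run-sheet times are still needed.
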